Vital signs		Notable abnormalities	
		Absolute	Relative to baseline
Pulse rate (beats/min)		> 130 < 40	> 120 and increase from baseline ≥ 15 ≤ 50 and decrease from baseline ≥ 15
Blood pressure (mmHg)	Systolic	> 200 < 75	≥ 180 and increase from baseline ≥ 20 ≤ 90 and decrease from baseline ≥ 20
	Diastolic	> 115 < 40	≥ 105 and increase from baseline ≥ 15 ≤ 50 and decrease from baseline ≥ 15

Note: these notable ranges should not be used as reference ranges to establish a clinical diagnosis

[figure not shown]

14 Appendix 2: Liver Monitoring and Follow-up Requirements

For transaminases (ALT, AST, GGT) and bilirubin, the baseline value will be calculated as the mean of the last two assessments before first administration of the study drug, which are usually those taken at the Screening 2 and Baseline visit.

Table 14-1 Management of Subjects with Confirmed ALP, ALT, AST, or Bilirubin Elevations With or Without Liver Related Clinical Symptoms

Baseline	Treatment-Emergent (Confirmed ^a)	Liver-Related Clinical Symptoms ^b	Action taken	
			Monitoring ^c	Study Drug
ALT and/or AST				
Baseline ALT and/or AST < 2 × ULN	ALT and/or AST > 3 × ULN but ≤ 5 × baseline	None	Laboratory monitoring and causality evaluation	Continue dosing
		Present	Comprehensive clinical evaluation and laboratory monitoring, as well as causality evaluation ^d , [REDACTED]	Interrupt dosing ^e
	ALT and/or AST > 3 × ULN but ≤ 5 × baseline AND total bilirubin > 2 × ULN (in Gilbert's syndrome, see footnote ^f)	With or without liver-related clinical symptoms	Comprehensive clinical evaluation and laboratory monitoring, as well as causality evaluation ^d , [REDACTED]	Interrupt dosing ^e
	ALT and/or AST > 3 × ULN and > 5 × baseline	With or without liver-related clinical symptoms	Comprehensive clinical evaluation and laboratory monitoring, as well as causality evaluation ^d , [REDACTED]	Permanently discontinue
Baseline ALT and/or AST ≥ 2 × ULN	ALT and/or AST > 2 × baseline but ≤ 3 × baseline	None	Laboratory monitoring and causality evaluation	Continue dosing
		Present	Comprehensive clinical evaluation and laboratory monitoring, as well as causality evaluation ^d , [REDACTED]	Interrupt dosing ^e
	ALT and/or AST > 2 × baseline but ≤ 3 × baseline AND total bilirubin > 2 × ULN ^f	With or without liver-related clinical symptoms	Comprehensive clinical evaluation and laboratory monitoring, as well as causality evaluation ^d , [REDACTED]	Interrupt dosing ^e

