Baseline	Treatment-Emergent (Confirmed ^a)	Liver-Related Clinical Symptoms ^b	Action taken	
			Monitoring ^c	Study Drug
	ALT and/or AST > 3 × baseline	With or without liver-related clinical symptoms	Comprehensive clinical evaluation and laboratory monitoring, as well as causality evaluation ^d , [REDACTED]	Permanently discontinue
Baseline normal or elevated ALT and/or AST values	ALT and/or AST > 3 × ULN and > 2 × baseline AND either total bilirubin > 2 × baseline OR INR increase by >0.3 to a value >1.5	With or without liver-related clinical symptoms	Comprehensive clinical evaluation and laboratory monitoring, as well as causality evaluation ^d , [REDACTED]	Interrupt dosing ^e
ALP				
Baseline ALP ≤ ULN	ALP > 1.5 × ULN (not due to known bone pathology)	None	Laboratory monitoring and causality evaluation ^c	Continue dosing
		Present	Comprehensive clinical evaluation and laboratory monitoring, as well as causality evaluation ^d , [REDACTED]	Interrupt dosing ^e
	ALP > 1.5 × ULN (not due to known bone pathology) AND total bilirubin > 2 × ULN ^f	With or without liver-related clinical symptoms	Comprehensive clinical evaluation and laboratory monitoring, as well as causality evaluation ^d , [REDACTED]	Interrupt dosing ^e
Baseline ALP > ULN	ALP > 2 × baseline (not due to known bone pathology)	None	Laboratory monitoring and causality evaluation ^c	Continue dosing
		Present	Comprehensive clinical evaluation and laboratory monitoring, as well as causality evaluation ^d , [REDACTED]	Interrupt dosing ^e
	ALP > 2 × baseline (not due to known bone pathology) AND total bilirubin > 2 × ULN ^f	With or without liver-related clinical symptoms	Comprehensive clinical evaluation and laboratory monitoring, as well as causality evaluation ^d , [REDACTED]	Interrupt dosing ^e

Baseline	Treatment-Emergent (Confirmed ^a)	Liver-Related Clinical Symptoms ^b	Action taken	
			Monitoring ^c	Study Drug
Total or Direct Bilirubin				
Baseline total bilirubin ≤ ULN	Total bilirubin > 2 × ULN ^f	With or without liver-related clinical symptoms	Comprehensive clinical evaluation and laboratory monitoring, as well as causality evaluation ^d , [REDACTED]	Interrupt dosing ^e
Baseline total bilirubin > ULN	Total bilirubin > 1.5 × baseline ^f	With or without liver-related clinical symptoms	Comprehensive clinical evaluation and laboratory monitoring, as well as causality evaluation ^d , [REDACTED]	Interrupt dosing ^e

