## **5.3 Laboratory parameters derivations**

### **5.3.1 Laboratory parameters**

Liver laboratory events will be classified in two ways:

- Events as defined in Appendix 2 of the protocol (Table 14-1). Only the laboratory results criteria will be considered. Confirmation of the results is not taken into account. For Table 14-1, criteria of ALT and AST are evaluated as either-or relationship, while those of baseline and treatment-emergent assessments as both-and relationship.
- Events as defined in the internal Novartis “Analysis plan for liver safety data”, Table 6-1.

[figure not shown]
Renal laboratory events will be classified in two ways:

- Events as defined in Appendix 3 of the protocol (Table 15-1). Only the laboratory results criteria will be considered. Confirmation of the results is not taken into account.
- Events as defined in the internal Novartis “Analysis plan for renal safety data”,

Criteria for other laboratory parameters:

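### SAP 5.3.1 does not require the same enzyme to meet both the baseline and the on-treatment condition of Table 14-1, so one liver-event criterion can count patients with no rise

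*SAP*

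**What the plan says.** SAP 5.3.1 classifies liver laboratory events in two ways: by protocol Table 14-1, and by an internal sponsor plan that is not in the documents. For Table 14-1 it uses the laboratory criteria only and does not require confirmation of a value. It adds that "criteria of ALT and AST are evaluated as either-or relationship, while those of baseline and treatment-emergent assessments as both-and relationship".

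In protocol Appendix 2, Table 14-1, the ALT/AST rows form two baseline groups and one row for any baseline:

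- Group 1, "Baseline ALT and/or AST < 2 × ULN": on treatment, either "ALT and/or AST > 3 × ULN but ≤ 5 × baseline" (a further row adds total bilirubin above 2 × ULN) or "ALT and/or AST > 3 × ULN and > 5 × baseline".
- Group 2, "Baseline ALT and/or AST ≥ 2 × ULN": on treatment, either "ALT and/or AST > 2 × baseline but ≤ 3 × baseline" (again with a bilirubin variant) or "ALT and/or AST > 3 × baseline".
- Any baseline: "ALT and/or AST > 3 × ULN and > 2 × baseline", together with a bilirubin or INR condition.

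Protocol exclusion criterion 14 rules out ALT or AST only above 5 × ULN. SAP 2.8.1 plans absolute and relative frequencies of patients with these liver events.

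**The concern.** The SAP sentence names two logical operations, OR across enzymes and AND across time points, but not their order. The order decides the result:

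- Cell by cell: (ALT or AST meets the baseline condition) AND (ALT or AST meets the on-treatment condition).
- Enzyme by enzyme: (ALT meets both conditions) OR (AST meets both conditions).

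The table's layout, with ALT and/or AST repeated in each cell, invites the first. Under it, AST can supply the baseline condition and ALT the on-treatment condition. A patient who entered with raised ALT and lower AST could then be tabulated as a treatment-emergent liver event although nothing rose.

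Safety is the primary objective, and protocol section 1.1 notes that both drugs may raise transaminases with a possible additive effect. A liver-event count that depends on the programmer's reading is undesirable here.

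**Working it through.** The plan gives no figure on this point, so there is none to reproduce. The check has three parts. Values are in multiples of ULN, and each on-treatment value is compared with that enzyme's own baseline.

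**1. Single patients**

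| Baseline ALT / AST | On treatment ALT / AST | Cell by cell | Enzyme by enzyme |
|---|---|---|---|
| 4.0 / 1.5 | 4.0 / 1.5 (unchanged) | event | no event |
| 4.8 / 1.5 | 3.2 / 1.2 (both fall) | event | no event |
| 4.0 / 2.5 | 4.0 / 2.5 (unchanged) | no event | no event |
| 1.5 / 1.2 | 3.5 / 1.2 (ALT rises) | event | event |

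In row 2, AST 1.5 < 2 meets the group 1 baseline condition. ALT 3.2 > 3 and 3.2 ≤ 5 × 4.8 = 24 meets the on-treatment condition. Both baselines are allowed at entry.

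**2. Which rows can be met without a rise**

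Take all pairs of baselines from 0.3 to 5.0 in steps of 0.1 (48 × 48 = 2,304 pairs), with on-treatment values equal to baseline.

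- Cell by cell, an unchanged pair meets "ALT and/or AST > 3 × ULN but ≤ 5 × baseline" when one enzyme is below 2 (17 grid values) and the other above 3 (20 grid values): 2 × 17 × 20 = 680 of 2,304 pairs.
- Enzyme by enzyme, no pair does. One enzyme would have to go from below 2 to above 3, which is more than a 3/2 = 1.5-fold rise.
- Every other ALT/AST row requires more than 2, 3 or 5 times baseline. No unchanged pair meets any of them under either reading.

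The 680 shows where the problem lies. It is not a prevalence, because patients are not spread evenly over the grid.

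**3. Illustrative size**

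The documents give no baseline distribution of ALT or AST, so everything here is assumed. Baselines are lognormal and values above 5 × ULN are removed. The counts are for "ALT and/or AST > 3 × ULN but ≤ 5 × baseline" in group 1.

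*Static values, no change.* Median ALT 1.2–2.0, median AST 0.75 times that, log-SD 0.5–0.6, correlation 0.70–0.85.
- By cell: 1.1–8.3%. In an arm of 50 this is 0.011 × 50 ≈ 0.5 to 0.083 × 50 ≈ 4.2 patients.
- By enzyme: 0%.

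*Visit-to-visit variation.* Table 6-1 has 10 post-baseline liver tests (Weeks 2, 4, 8, 12, 16, 24, 32, 40, 48 and 52). Baseline is the mean of two values. Median ALT 1.2–2.0, AST/ALT 0.72, log-SD 0.55, correlation 0.8, 200,000 patients per scenario.

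| Scenario | By cell | By enzyme |
|---|---|---|
| No true change, within-patient log-SD 0.15 | 7–17% | 0.4–0.9% |
| No true change, within-patient log-SD 0.22 | 11–24% | 3–6% |
| 26% fall in both enzymes, log-SD 0.15–0.22 | about 1.4–8.3% | 0–0.4% |

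Without true change, the excess by cell over by enzyme runs from about 7 − 0.4 = 6.6% to 24 − 6 = 18%, or about 3 to 9 patients per arm of 50. Widening the assumptions (log-SD 0.4–0.6, correlation 0.7–0.95) gives 9–25% by cell at log-SD 0.22 and 4–18% at 0.15.

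In these runs about 14–30% of patients have one enzyme below and one at or above 2 × ULN at baseline.

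**The case against.** The strongest objection is that the SAP does not state a mixed-enzyme rule. Its sentence reads equally well enzyme by enzyme. The on-treatment thresholds expressed as multiples of baseline favour that reading, since a value is naturally compared with the same enzyme's baseline. This stands: the defect is an undetermined derivation. It still needs settling, because the two readings give different counts and the table's layout points towards the one that goes wrong.

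Scope and consequence are also limited, and this stands too:

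- No-rise flags arise only under "ALT and/or AST > 3 × ULN but ≤ 5 × baseline". Its bilirubin variant also needs total bilirubin above 2 × ULN.
- The study tests no safety hypothesis, and the table is descriptive.
- Shift tables, changes from baseline and a second liver classification are also reported, and possible drug-related liver injury is adjudicated blind. The second classification cannot be relied on as a remedy, because its content is not in the documents.

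A reader might infer that the whole liver-event table is contaminated, including the rows that lead to permanent discontinuation. Part 2 of the check shows otherwise.

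A reader might also infer that false flags outnumber true ones or dilute differences between arms. Neither has been shown, because the simulations contain no true liver events and compare no arms. Protocol section 1.1 reports that tropifexor lowered transaminases, and it is in three of the four arms. False flags could therefore differ between arms, but the documents give no distributions from which to size this.

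Finally, the 3–6% flagged by enzyme at the larger variation comes from unconfirmed single values, which is a separate choice in the SAP.

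**Conclusion.** The point holds as an ambiguity with a real consequence. SAP 5.3.1 leaves open whether one enzyme must meet both conditions, and under the cell-by-cell application eligible patients with unchanged or falling enzymes count under one criterion of Table 14-1. The logic is certain; the size is not.

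Under assumed distributions with no true change, about 1–8% of patients are flagged by cell with static values and roughly 7–25% with variation over 10 visits, going down to 4% under the most favourable assumptions tried. By enzyme the figures are 0% and about 0.4–7%. With a 26% fall in both enzymes and visit-to-visit variation, about 1–8% are flagged by cell against under 0.5% by enzyme. No formal test is affected, but a planned table serving the primary safety objective could be wrong.

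A related gap lies in the protocol. A patient whose enzymes straddle 2 × ULN satisfies both "Baseline ALT and/or AST < 2 × ULN" and "Baseline ALT and/or AST ≥ 2 × ULN". The lowest rows and the bilirubin rows of the two groups carry the same actions, but the permanent-discontinuation thresholds differ. With baseline ALT 2.5 and AST 1.5, for example, an AST of 6.0 is 6.0 / 1.5 = 4 times baseline. It falls under "ALT and/or AST > 3 × ULN but ≤ 5 × baseline" in one group and "ALT and/or AST > 3 × baseline" in the other.

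**What to change.** Replace the SAP sentence with: *ALT and AST are evaluated separately; the baseline and treatment-emergent conditions must be met by the same enzyme, each on-treatment value being compared with that enzyme's own baseline; a patient has an event if either enzyme qualifies.*

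This costs one sentence and one change to the derivation code, with no new data. It also settles, for the tabulation, which baseline group each enzyme belongs to.

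The SAP sentence does not change the protocol table. The overlapping baseline groups of Table 14-1 and their differing actions must be reconciled there; no clinical action is proposed here.

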**Table 5-1**      **Notable criteria for other laboratory parameters**

Parameter	Threshold value	Unit
Albumin	<32	g/L
Hemoglobin	<70	g/L
Hemoglobin	>200	g/L
White blood cell count	<2.0	10  /L
White blood cell count	>35.0	10  /L
Platelets	<50	10  /L
Platelets	>1000	10  /L
Prothrombin Time INR	>4.0	
PT	>40.0	sec
APTT	>80.0	sec
Sodium	<120	mmol/L
Sodium	>160	mmol/L
Potassium	<3.0	mmol/L
Potassium	>6.0	mmol/L
Glucose	<2.2	mmol/L
Glucose	>27.8	mmol/L
Calcium	<1.50	mmol/L
Calcium	>3.00	mmol/L
Phosphate	<0.29	mmol/L
Creatinine	>177	μmol/L
Calculated eGFR	<60	mL/min

[figure not shown]

### 5.3.5 Derived baseline characteristics

#### Use of lipid reducing drugs (e.g. statins)

Concomitant use of statins is determined as follows:

If drug belonging to ATC code C10 was used either starting prior to randomization and ongoing at randomization, or starting during the treatment epoch, concomitant use of statins is considered Yes, otherwise No.

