3.5 Purpose and timing of interim analyses/design adaptations

3.6 Risks and benefits

As well as the risks and potential risks described in the tropifexor and CVC (TBR-652) Investigators' Brochures, there may be unknown risks to tropifexor and CVC which may be unforeseen.

Tropifexor

Based on the mechanism of action of tropifexor as a highly potent and specific agonist of the Farnesoid X Receptor (FXR) and data acquired in the First-in-Human study CLJN452X2101 and in nonclinical toxicology studies the risk-benefit assessment of tropifexor is as follows:

Transient and asymptomatic increases in ALT have been identified as an adverse reaction to tropifexor in healthy volunteers. Potential toxicities to be considered for tropifexor include more severe liver effects, gastrointestinal effects, coagulation effects, renal function abnormalities, and embryo-fetal toxicity. In addition it is anticipated that tropifexor may have pharmacodynamic effects on drug metabolism and elimination. Guidelines for the evaluation and detection of these potential toxicities and for their management and for minimization of risk if they do arise are discussed in the tropifexor Investigator's Brochure.

Tropifexor treatment may have the anticipated benefits on biliary metabolism (reduced synthesis and increased detoxification), lipid profile (lowering triglycerides) and anti-fibrotic activities (reduced hepatic fibrosis) may improve pathophysiology and patient outcomes over longer term treatment in longer-term development studies.

In addition to usual study monitoring, patients' liver tests will be followed closely, especially early in therapy, in conjunction with the Data Monitoring Committee (DMC), including frequent checks of a liver safety panel and drug dosage dose reduced or discontinued if necessary.

Cenicriviroc

CVC is currently in Phase 3 clinical development for the treatment of liver fibrosis in adults with NASH and in Phase 2 development in subjects with primary sclerosing cholangitis (PSC). Overall, over 1000 subjects have been exposed to CVC in both ongoing and completed studies, with a maximum exposure available of ≥ 48 weeks of treatment in approximately 260 subjects. CVC doses ranged from 25 mg to 900 mg across all CVC studies.

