Patients on medications specified in [Table 5-4](#) can be included if the dose has been stable for at least 1 month before the baseline biopsy (historical or performed during screening).

A stable dose is defined as a dose within 25% of the baseline dose.

No new use of the medications in [Table 5-4](#) is allowed between 1 month before the baseline biopsy and until Study Completion.

Table 5-4 Medications permitted only if dose is stable within 25 percent of baseline dose

Medication
Oral anti-diabetic medications such as pioglitazone, metformin and/or sulfonylureas
GLP-1 agonists such as liraglutide, exenatide , lixisenatide, albiglutide or dulaglutide
Fibrates, niacin
Vitamin E
Pentoxifylline

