#### **2.4.2 Prior, concomitant, and post therapies**

Medications will be identified using the WHO dictionary including ATC code and presented for the SAF. Prior medications are defined as any medications taken prior to the first administration of study drug (regardless of whether they are stopped or continued after randomization). Concomitant medications and significant non-drug therapies are defined as those used during the double-blind period. Prior and concomitant medications will be summarized by treatment group in separate tables. Medications will be presented in alphabetical order, by ATC codes and grouped by anatomical main group (the 1st level of the ATC code, e.g. “Cardiovascular system”, C), and by the first subgroup, e.g. “Lipid modifying agents” (C10). Tables will also show the overall number and percentage of subjects receiving at least one drug of a particular ATC code and at least one drug in a particular anatomical main group and first subgroup.

Concomitant medications that were prohibited as per protocol and given between start and end of treatment period as well as significant non-drug therapies, and medications that are permitted only if the dose is stable within 25 percent of the baseline dose (Table 5-4 in the protocol) will be provided in separate tables.

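### The SAP's baseline statin flag counts any C10 lipid drug and any C10 drug first started on treatment; it needs splitting, although no visible primary or secondary analysis uses it

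*SAP*

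**What the plan says.** SAP 5.3.5 is headed "Derived baseline characteristics". Its one visible variable has a sub-heading about lipid-reducing drugs, with statins given as an example. The rule itself is narrower in name: "Concomitant use of statins is determined as follows". The value is Yes under this condition, and No otherwise: "If drug belonging to ATC code C10 was used either starting prior to randomization and ongoing at randomization, or starting during the treatment epoch".

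Other parts of the documents bear on this rule:

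- SAP 2.1 generally defines baseline as the last assessment before the first administration of study treatment.
- SAP 2.4.2 treats concomitant medication as medication used in the double-blind period. It gives C10 as its example of a first ATC subgroup and labels it "Lipid modifying agents".
- SAP 2.3 summarises baseline characteristics for the FAS by treatment group and in total.
- Protocol 5.5.8.1, Table 5-3, permits statins with caution, most of them with a dose ceiling. Table 5-4 permits "Fibrates, niacin" and some other drugs only at a stable dose. The bar on new use covers the drugs in Table 5-4, and statins are not in that table.

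**The concern.** The variable is filed as a baseline characteristic, but part of its definition looks forward into the randomised treatment period. It is named for statins, but it tests for a wider class.

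The timing matters because a drug start after randomisation can depend on the arm. Protocol 3.6 lists a possible tropifexor benefit on the lipid profile, naming lower triglycerides, and three of the four arms contain tropifexor. If starts differ by arm, a baseline table built on the flag can show a difference that randomisation did not produce. An exploratory subgroup or adjustment that used the flag would condition on something that happened after randomisation.

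The class matters because Protocol Table 5-3 warns that CVC may raise exposure to two named statins and asks for close monitoring of patients taking them. Three of the four arms contain CVC. A flag that mixes statin and non-statin users cannot pick out statin users for an exploratory look at safety.

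**Working it through.** The plan states no figure here, so there is none to reproduce. The check applies the rule to each kind of patient and compares the result with what the labels promise.

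| C10 drug ongoing at randomisation | C10 drug started on treatment | Flag | Baseline statin user? | Result |
|---|---|---|---|---|
| Statin | None | Yes | Yes | Correct |
| Statin and fibrate | None | Yes | Yes | Correct |
| Fibrate or niacin only | None | Yes | No | Wrong class |
| None | Statin | Yes | No | Wrong as baseline; right as on-treatment statin use |
| None | Non-statin C10 drug | Yes | No | Wrong on both |
| None | None | No | No | Correct |

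**Class.** The third row follows from the SAP's own label for C10, which covers lipid-modifying agents as a group. It assumes that fibrates and niacin are coded there, as that label implies. Table 5-4 lets such patients into the trial.

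**Timing.** The fourth row can occur because the bar on new use does not reach statins. The fifth row is less likely for fibrates and niacin, since new use of Table 5-4 drugs is not allowed.

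**Size.** The documents give neither the share of patients on a C10 drug at randomisation nor the share who start one later. Let b be the share with a C10 drug ongoing at randomisation, the same in two arms, and let s be the share of the remaining patients who start one on treatment. Then:

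- flag prevalence in an arm = b + (1 − b) × s
- spurious difference between arms = (1 − b) × (s₁ − s₂)

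Take b = 0.40, with s = 0.15 or 0.02. All three values are assumptions.

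- s = 0.15: 0.40 + 0.60 × 0.15 = 0.49
- s = 0.02: 0.40 + 0.60 × 0.02 = 0.412
- Unequal starts, 0.15 against 0.02: 0.49 − 0.412 = 0.078, or 7.8 points. With 50 patients per arm that is 0.078 × 50 = 3.9 patients.
- Equal starts at either rate: a difference of 0. The flag still overstates baseline use in both arms, by 0.60 × 0.02 = 1.2 points or 0.60 × 0.15 = 9 points.

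On these assumptions the spurious difference runs from 0 to 7.8 points. The class error is separate: it adds to apparent statin use the share of patients whose only C10 drug is not a statin, and the documents do not give that share.

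**Where the flag is used.** The primary safety analysis is descriptive and has no model (SAP 2.5.2). The CMH test controls only for baseline fibrosis stage (SAP 2.7.2). The visible imputation covariates in SAP 5.1.4 are treatment group, baseline fibrosis stage, baseline ALT and change in ALT; part of that list is blacked out. Subgroup analyses are left to data exploration (SAP 2.2). The flag is named in none of these.

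**The case against.** The strongest defence is that the rule is coherent under another name. The sub-heading speaks of lipid-reducing drugs, which fits C10, and the word concomitant fits on-treatment use as SAP 2.4.2 defines it. Read this way, the rule is a sound concomitant lipid-drug flag with a wrong name and in the wrong section. That explains how the text may have come about, but it does not rescue the rule. A programmer who follows 5.3.5 as written produces a variable called statin use, files it with baseline characteristics, and gets the wrong values shown above.

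The defence is right about several stronger readings that a reader might infer:

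- *That the flag biases the trial's results.* No visible primary or secondary analysis uses it, and SAP 2.3 does not name it among the variables to be tabulated. Use in a blacked-out section can be neither shown nor ruled out.
- *That information on new lipid treatment is lost.* SAP 2.4.2 already tabulates prior and concomitant medication by arm down to the C10 level, and Table 5-4 drugs separately. Those tables do not isolate new starts, so a flag for them would add to what is reported.
- *That every non-statin user and every new starter is misclassified.* A fibrate user who also takes a statin is coded correctly, and someone who starts a statin on treatment is a correct Yes for concomitant use.
- *That sites may start statins without restraint.* Table 5-3 drugs are for use if needed, with caution, at low dose and for a short time. Protocol 5.5.7 requires each concomitant drug to be assessed individually.

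**Conclusion.** The point holds as a faulty derivation rule with limited reach. It codes post-randomisation starters as users on a baseline variable, and users of only non-statin C10 drugs as statin users. Both errors follow from the text alone and need no assumed rate.

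The consequence is confined to the descriptive baseline summary by arm, if the flag is shown there, and to any exploratory subgroup or adjustment that takes it up. The size cannot be derived from the documents. The 7.8-point figure shows how the rule works under assumed rates and is not a forecast: the protocol's cautious remark about triglycerides does not support a gap of 15% against 2%. In comparisons of a combination with tropifexor alone both arms contain tropifexor, so that route to unequal starts is weaker. With equal use at randomisation and equal starts the distortion between arms is zero, although the flag's level is still too high as a measure of baseline use.

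The rule should be corrected because it contradicts the SAP's own definitions and the correction is cheap. Nothing visible suggests that it threatens the primary or secondary conclusions.

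**What to change.** Replace the single flag in SAP 5.3.5 with three variables:

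- (a) Baseline statin use: a C10 drug that contains a statin, including fixed combinations, started before and ongoing at first dose.
- (b) Baseline use of other lipid-modifying drugs: any other C10 drug, with the same timing.
- (c) New lipid-modifying drug on treatment: a C10 drug first started after first dose, reported by arm to supplement the concomitant-medication tables of SAP 2.4.2.

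State that only (a) and (b) may be used as baseline characteristics, subgroup factors or covariates.

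The cost is a change of SAP wording and a short derivation. The medication data are already coded to ATC, no clinical rule changes, and no visible primary or secondary output is affected. The downside is one extra table.
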